10.1 Sample Size Determination

A total sample size of 672 subjects (224 per trial arm, and 336 per country) will be necessary to achieve 90% power to detect a non-inferiority margin difference of 15%, assuming that the standard regimen failure rate is 10% and the intervention regimen is 12%, for a one-sided Z test at a significance level of 0.025. This total sample size has been increased in anticipation in 40% to assure a minimum 60% of participants with active infection (positive PCR) and further by 10% to account for potential losses to follow-up, in order to maintain the specified power and inferiority/superiority margins. This means that individuals removed from the study for the reasons mentioned will not be replaced. This sample size will allow the study to also demonstrate a superiority margin of difference of 10% with 80% power regarding the safety of the experimental arm. Considering the percentage of treatment interruption for conventional treatment of 20%, and a reduction of 50% in the experimental arm, power of 90% and $\alpha=0.05$, 197 patients will be needed in each arm.

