A control event rate is expected to be 10% of treatment failure (at least one positive PCR during follow up period) and a 20% of treatment withdrawn due to any AE. Control arm showing posterior probability of superiority of 97.5% or higher will be considered superior. This will be calculated for the experimental intervention versus the control group based on the observed data at the time of interim assessment with a superiority p-value stopping boundary of 0.010.

The decision for interim analysis will be made in a blinded manner (e.g., based on pooled number of events).

All analyses will be performed using Stata 13.0 for Windows.

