10.4 Justification of Non-Inferiority Margin

A non-inferiority margin of 15% has been defined for our study. This means that a maximum acceptable difference in treatment failure rate of 15% with the comparator is considered the difference that would still result in a significant proportion of participants treated appropriately. Historical data on therapeutic failure in most randomized controlled trials is around 20% where the effectiveness rates were measured by parasitic DNA detection on peripheral blood. In adults the failure rate ranges between 10 and 40%. (30,31) If the placebo is considered, it would still be much more advantageous, since the failure rates range between 85 and 95%. (16,32)

For these reasons the study prefers to be conservative in choosing the non-inferiority margin, as the consequence of choosing a margin greater than the actual effect of the active control treatment in the study can be a false conclusion that a new regime is effective, and therefore have an undesirable result for public health. As the intention is treating participants with CD as a public health strategy for reducing the transmission of congenital transmission, reducing parasitemia, through an increase in adherence, a higher rate of compliance in addition to a reduction in costs programmatic level is intended.

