10.8 Efficacy Analysis

The primary efficacy endpoint is parasitological response, defined as sustained parasitological clearance at 24 months of follow-up after treatment, determined by serial qualitative PCR results. The primary analysis will be the comparison of the sustained parasitological clearance of each treatment arm. An efficacy interim analysis will be performed when participants complete 12 months from end of treatment. The stopping rule will be applied with no change planned on the sample size. At that point, if the condition of suspending the study is accomplished, participants will be considered as early treatment failures. Secondary efficacy analyses will further characterize differences in therapeutic response within this trial, namely:

- Parasite clearance at 6, 12 and 18 months.
- Serological response by conventional serology assessed at baseline and at 24 months of follow up after treatment.

For efficacy assessments, the EOT of each treatment arm will be defined according to the duration of the arm dosing regimen.

For PCR analyses, means and 95% confidence intervals will be presented per group and visit. In addition, time to sustained parasite clearance until 6, 12, 18 and 24 months of follow-up visits will be assessed using Kaplan– Meier survival analysis with log rank test for significance. Repeated measures analysis will also be performed. Multivariate analysis including those variables with a p-value<0.20 in the univariate model will be performed to define early and late predictors of a sustained parasitological response. The backwards method will be used to remove the variables that presented p-value greater than 0.05 in the multivariate analysis, until the obtention of the final model.

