Reasons for early termination by the PI may be:

- Insufficient time or resource to conduct the study;
- Lack of eligible participants.

Stopping rules will be clearly defined for futility:

- Regarding efficacy, a stopping rule is defined by significant difference compare to standard treatment measured through the detection of parasite DNA at 12 months after EOT. The stopping rule will be applied with no change planned on the sample size. Participants will be considered

early treatment failures.

If a study is terminated early either by the Sponsor or by the investigator, the investigator must:

- Complete all CRFs to the greater extent possible;
- Return all test articles, CRF, and related study materials to the Sponsor who provided them;
- Answer all questions of the Sponsors or their representatives related to data of participants enrolled at the site prior to study termination;
- Ensure that participants enrolled in the study who had not yet reached a follow up time point are followed up with the necessary medical care;
- Provide in writing the reasons for his decision to the national health authority and the Sponsor.

15. Ethics

The protocol for this study has been designed in accordance with the general ethical principles outlined in the Declaration of Helsinki and ICH guidelines for GCP (International committee for Harmonization). Fiocruz assures that it will comply with all applicable state, local and regional laws for protecting the rights and welfare of human participants. This protocol and any protocol amendments will be reviewed/approved by the relevant IECs before its implementation.

This study will be submitted for review to WHO Ethics Review Committee (ERC), and to the national Ethical Committee boards in Bolivia and Colombia, shared with each of the collaborating institutions. Any modifications made to the protocol after receipt of the ERC approval must also be submitted by the investigator in writing to the IEC in accordance with local procedures and regulatory requirements.

16. Informed consent process

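### For a short arm that does worse, the 12-month stopping criterion tests against zero difference and ignores the 15-point margin, while section 4.1 states the opposite trigger

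*Protocol*

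**What the plan says.** **The objective.** Protocol 10.1 plans "A total sample size of 672 subjects (224 per trial arm, and 336 per country"), with a 15-point margin, 10% failure on standard and 12% on a short regimen, "for a one-sided Z test at a significance level of 0.025". Section 10.4 explains the margin as "a maximum acceptable difference in treatment failure rate of 15% with the comparator". The primary endpoint is sustained negative PCR at 24 months after treatment (sections 3 and 10.8).

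**The interim.** Section 10.3 bases early stopping on superiority, once all participants have reached 12 months after treatment. It then states: "Control arm showing posterior probability of superiority of 97.5% or higher will be considered superior". The next sentence adds a superiority p-value boundary of 0.010, without saying whether it is one- or two-sided. Section 14 lists the efficacy rule under futility: "a stopping rule is defined by significant difference compare to standard treatment", measured by parasite DNA at 12 months. Section 10.8 adds that "if the condition of suspending the study is accomplished, participants will be considered as early treatment failures", and section 14 repeats the early-failure classification. None of these places mentions the margin.

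**The other wording.** Section 4.1 says the study may be interrupted if the experimental arms are superior to control on treatment failure. It leaves the monitoring bounds to an interim monitoring plan and gives the DSMB a helping role in the decision.

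**The concern.** In a non-inferiority trial, futility means that the trial is unlikely to show the short arm to be within the margin. A test against zero asks a different question. A short arm can be significantly worse than control and still have its whole confidence interval below 15 points. For such an arm the futility label in section 14 is wrong, and the criterion in 10.3 can conflict with the success criterion in 10.1 and 10.4.

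At stake is a recommendation to close an arm before its 24-month endpoint when its data so far lie inside the difference that the protocol calls acceptable. The classification in 10.8 and 14 makes this worse. As worded, it follows from the stopping condition and not from a participant's own PCR results, so it could alter the primary endpoint itself.

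**Working it through.** **1. Inputs.** From the protocol: 224 per arm, control failure 10%, short-arm failure 12%, margin 15 points, one-sided 0.025, 90% power, at least 60% PCR-positive, 10% loss (10.1); all randomised analysed (10.3); 97.5% posterior and p 0.010 (10.3). Assumed, because not stated: independent Beta(1,1) priors for the interim posterior, and the same failure rates at 12 and 24 months.

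**2. The plan's own sample size.** n = (1.960 + 1.282)² × (0.10×0.90 + 0.12×0.88) / (0.15 − 0.02)² = 121.6, so 122 per arm. Then 122 / 0.6 × 1.1 = 223.7, so 224. The stated figure reproduces.

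**3. One dataset that meets everything.** Control 22/224 (9.8%), short arm 41/224 (18.3%).
- Difference 19/224 = 8.5 points. Unpooled SE = √[(0.0982×0.9018 + 0.1830×0.8170)/224] = 0.0326. The 95% interval is 8.48 ± 1.96 × 3.26, or 2.1 to 14.9 points. The upper limit is below 15, so the non-inferiority criterion is met on these data.
- Pooled rate 63/448 = 0.1406. z = 0.0848 / √(0.1406×0.8594×2/224) = 2.58. Two-sided p = 0.0098, so the 0.010 boundary is met on either reading.
- Posterior probability that control is better, Beta(42,184) against Beta(23,203): 0.995, above 0.975.

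With 22/224 on control, both verdicts occur for 36 to 41 short-arm failures under the 97.5% rule, for 39 to 41 at one-sided 0.010, and for 41 only at two-sided 0.010.

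**4. How often.** Sum over all failure counts x (control) and y (short arm): Σ Bin(x; 224, 0.10) × Bin(y; 224, p) × I(criterion met). Non-inferior means that the upper 95% Wald limit is below 15 points. The 17.2% scenario is the complement of the 82.8% two-week result cited in section 2.2.

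| Criterion | Measure | p = 12% | p = 15% | p = 17.2% |
|---|---|---|---|---|
| 97.5% posterior | met | 9% | 35% | 60% |
| | met and non-inferior | 9% | 24% | 28% |
| p 0.010, one-sided | met | 5% | 23% | 46% |
| | met and non-inferior | 4% | 12% | 14% |
| p 0.010, two-sided | met | 3% | 16% | 36% |
| | met and non-inferior | 2% | 6% | 6% |

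The posterior rows move by about one point depending on whether the Beta posterior is approximated or evaluated exactly.

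**5. Where the overlap shrinks.**
- With 202 per arm (224 × 0.9), the two-sided 0.010 overlap is 1.2%, 2.3% and 1.7% in the three scenarios.
- With PCR-positive participants only (224 × 0.6 = 134, or 122 after loss), it is about 1% or less under every reading.
- With control failure at 20% (45/224), no short-arm count meets both.
- With control at 11/224 (4.9%), it widens to 27 to 32 failures even at two-sided 0.010.

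**The case against.** **Direction.** Section 4.1 gives the only explicit condition for interruption, and it concerns a better short arm, for which zero is the right null. The quoted sentence in 10.3 is followed by one that computes the probability for the experimental intervention against control, so the words naming the control arm may be a slip. This stands in part: direction has to be settled first. It does not remove the point, because the futility heading in section 14 and the early-failure classification in 10.8 and 14 make sense only for a worse short arm, and section 14 also sets its rule against standard with no margin.

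**Force.** Section 4.1 says the study may be interrupted, gives the DSMB a helping role and defers the bounds to a separate plan. This stands. A reader might infer that the trial will drop acceptable arms, or that the 90% power is lost by the rates in the table. The documents do not support either: the rates say how often the criterion is met, not how often an arm closes.

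**Timing.** A reader might infer that such an arm has already shown non-inferiority. It has not. Section 10.3 counts any positive PCR during follow-up as failure, so failures accumulate to month 24, and a 12-month interval below 15 points does not establish the 24-month result.

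**Size.** The larger figures depend on the 97.5% rule and on analysing all randomised participants. The 17.2% scenario is a 6-month result from a phase II arm of about 30, and that trial's 8-week arm failed at 10.7%. With 10.7% on control, the criterion is met about 50% of the time under the 97.5% rule and about 27% at two-sided 0.010. These limits stand and are why all three readings are shown.

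**Conclusion.** The point holds as a wrongly stated rule. For a short arm that does worse, 10.3 and section 14 test against zero, section 14 calls the result futility, and neither refers to the margin in 10.1 and 10.4. Section 4.1 contradicts them on direction. On the all-randomised set the criterion can be met by data that also meet the 15-point criterion at that time. The overlap runs from 2% (planning rates, two-sided 0.010) to 28% (17.2% failure, 97.5% posterior), and is about 1% or less if only PCR-positive participants are analysed. These sizes rest on 10% control failure, equal rates at 12 and 24 months, and the assumed Beta(1,1) priors. The mismatch between the rule and the objective rests on none of them. This is not a detail left to the analysis plan: the protocol itself fixes the thresholds and the label.

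**What to change.** - Reconcile 4.1, 10.3, 10.8 and section 14 on direction, on the governing threshold (97.5% posterior or p 0.010, with sidedness) and on the null value.
- For a worse short arm, replace the significant-difference futility wording with a non-binding rule on the margin scale. An example is a low conditional or predictive probability of meeting the 15-point criterion at 24 months, with the cut-off and the assumption about failures between months 12 and 24 both stated. Requiring significant inferiority beyond the margin would rarely act: at two-sided 0.010 with 22/224 on control it needs about 78/224 failures (difference 56/224 = 25.0 points).
- If a rule for a better short arm is kept, state it separately, against zero.
- Remove the statement in 10.8 and 14 that stopping makes participants early treatment failures, so that failure follows from PCR results.

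The cost is wording in the protocol and the DSMB charter. A non-binding futility rule needs no alpha adjustment and no extra participants. The downside is that an arm worse than control but inside the margin is followed to month 24; this adds no study-drug exposure, since dosing has ended by the interim.

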10.4 Justification of Non-Inferiority Margin

A non-inferiority margin of 15% has been defined for our study. This means that a maximum acceptable difference in treatment failure rate of 15% with the comparator is considered the difference that would still result in a significant proportion of participants treated appropriately. Historical data on therapeutic failure in most randomized controlled trials is around 20% where the effectiveness rates were measured by parasitic DNA detection on peripheral blood. In adults the failure rate ranges between 10 and 40%. (30,31) If the placebo is considered, it would still be much more advantageous, since the failure rates range between 85 and 95%. (16,32)

For these reasons the study prefers to be conservative in choosing the non-inferiority margin, as the consequence of choosing a margin greater than the actual effect of the active control treatment in the study can be a false conclusion that a new regime is effective, and therefore have an undesirable result for public health. As the intention is treating participants with CD as a public health strategy for reducing the transmission of congenital transmission, reducing parasitemia, through an increase in adherence, a higher rate of compliance in addition to a reduction in costs programmatic level is intended.

10.5 Participant Disposition

At the end of the study the following will be described:

- Number of participants screened;
- Number of participants assessed for eligibility excluded from the study, including reasons for exclusion;
- Number of participants who have been randomized in the study, as per original allocation (ITT set);
- Number of participants randomized into each study arm;
- Number and percentage of participants who have received at least one dose of study medication(s) (safety population – All Treated Set), per study arm;
- Number and percentage of participants who have received a full course of treatment and have completed EOT assessments (treatment completers), per study arm;
- Number and percentage of participants who have completed the study per study arm (study completers);
- Number and percentage of participants lost to follow-up and reasons of loss, total and per study arm;
- Number and percentage of participants who have withdrawn from the study, per study arm and reasons for withdrawal;
- Number and percentage of participants excluded from analysis per study arm and reasons for exclusion;
- Number and percentage of participants with at least one protocol violation and nature of protocol violation (major, minor).

10.6 Baseline

The following baseline characteristics of the study population will be described:

- Age distribution;
- Gender distribution;
- Nationality and country(ies) of residence;
- Proportion of participants with positive PCR;
- Antibody titers assessed by conventional and selected non-conventional serology, per type of assay;
- EKG abnormalities will be described per treatment arm as the proportion of participants per type of EKG finding, clinical relevance and changes over time.

10.7 Treatment Compliance

This is a double blinded study and compliance will be considered according to treatment course. During

the study, treatment compliance will be monitored through follow- up visits, and all information will be registered in the appropriate section of the CRF. Treatment compliance will be presented in the study report, describing the number and percentage of participants who have and have not completed a full course of treatment per study arm, their intake of meals, and the reasons for treatment drop-out per study arm.

For participants who do not complete a full treatment course, mean time of exposure to the trial drug will be described per study arm.

10.8 Efficacy Analysis

The primary efficacy endpoint is parasitological response, defined as sustained parasitological clearance at 24 months of follow-up after treatment, determined by serial qualitative PCR results. The primary analysis will be the comparison of the sustained parasitological clearance of each treatment arm. An efficacy interim analysis will be performed when participants complete 12 months from end of treatment. The stopping rule will be applied with no change planned on the sample size. At that point, if the condition of suspending the study is accomplished, participants will be considered as early treatment failures. Secondary efficacy analyses will further characterize differences in therapeutic response within this trial, namely:

- Parasite clearance at 6, 12 and 18 months.
- Serological response by conventional serology assessed at baseline and at 24 months of follow up after treatment.

For efficacy assessments, the EOT of each treatment arm will be defined according to the duration of the arm dosing regimen.

For PCR analyses, means and 95% confidence intervals will be presented per group and visit. In addition, time to sustained parasite clearance until 6, 12, 18 and 24 months of follow-up visits will be assessed using Kaplan– Meier survival analysis with log rank test for significance. Repeated measures analysis will also be performed. Multivariate analysis including those variables with a p-value<0.20 in the univariate model will be performed to define early and late predictors of a sustained parasitological response. The backwards method will be used to remove the variables that presented p-value greater than 0.05 in the multivariate analysis, until the obtention of the final model.

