3.1 Assessment of Efficacy

Efficacy of study treatment will be assessed by comparing the parasitological clearance rate, determined by sustained parasitological clearance until 24 months of follow-up after treatment. Secondary assessments of PCR will be conducted at 1, 4, 6, 8, 12 and 18 months

As this is a double-blind study, this will not interfere with the schedule of events, since all participants will have all required samples planned at each visit. In addition, a qualitative and quantitative efficacy assessment will be performed, correlating incidence of and time to parasitological clearance with changes in *T. cruzi* serology.

The study manual of operations will provide full details regarding procedures for blood samples (tube types and number, aliquots volume), handling, storage, and shipment of the samples for laboratory evaluation. Quality assurance systems will be in place and described. Training of personnel in each of the activities described above will take place before initiation of this clinical trial. All parasitological and other

laboratory assessments will be performed blinded to treatment allocation. The PCR samples will all be evaluated by trained specialists in a central laboratory in each country, using harmonized protocols, and similar techniques. Quality control will be carried out in the two countries by the same team of molecular biology specialists.

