6.1 Doses and treatment regimens

Subjects will be randomly assigned into one of the following balanced groups:

- **Group A (B300/2)** - BZN (Abarax®, tablet 100mg), 300 mg - 2 weeks: BZN 300 mg, divided in three daily doses, for 2 weeks matching with placebo tablet administered in three daily doses for 6 more weeks.
- **Group B (B300/4)** - BZN (Abarax®, tablet 100mg), 300 mg - 4 weeks: BZN 300 mg, divided in three daily doses, for 4 weeks matching with placebo tablet administered in three daily doses for 4 more weeks.
- **Group C (B300/8)** - BZN (Abarax®, tablet 100mg), BZN 300 mg, divided in three daily doses for 8 weeks.

BZN will be administered as 100mg tablets in blister packaging. Fixed doses of 300 mg will be used during the clinical trial. Participants will be advised that treatment must be taken in three divided doses, accompanied by a meal. During the visits throughout the treatment period, the subject will receive enough medication until the next scheduled visit. Participants are required to bring all remaining study drugs to the end of treatment (EOT) visit in order to check compliance with prescribed treatment and ensure drug accountability. As per recommendations in the BZN package insert, subjects will be advised to abstain from alcohol during treatment.

Placebo tablets will be provided by the same producer of Abarax® and will have the same size, format and include the same excipients as Benznidazol tablets formulation for oral administration. Quality control for both active treatment and placebo will be in charge of the manufacturer, Laboratorio ELEA.

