6.9.3 Neutropenia

Hematological assessments will be performed as previously described. If Absolute Neutrophil Counts \leq 1000 cells/ μ l are documented, treatment should be discontinued, and CBC will be repeated as soon as possible after the initial abnormality is identified. After that, the participant should be followed every 48 hours (2 days), or the closest possible interval, until the neutrophil counts increase above 1000 cells/mm or stabilize. The event should be immediately reported as an SAE.

In case Absolute Neutrophil Count is found to be $<$ 500 cells/ μ l, the treatment should be immediately interrupted, and a control hematological assessment is required within one day. Participants will be instructed to avoid exposure to people with respiratory tract infections and to respect general hygiene rules. Depending on profile (decreasing phase, stabilization phase, resolution phase), controls will be required every one to three days until normalization. The event should be immediately reported as an SAE.

In case Absolute Neutrophil Count is found to be $<$ 100 cells/ μ l, or below 1000 with associated fever (even of mild intensity) or infectious origin symptoms, the participant should immediately be hospitalized and reported as an SAE.

7. Laboratory assessment

Blood samples for hemogram and biochemistry (5mL each) will be collected in the same day at screening, at days 14 (allowable window of + 2 days), and 56 (allowable window of + 7 days).

Blood samples for serology will be collected at screening visit and at month 24 after EOT.

Blood samples for PCR will be collected at screening visit and at 1, 4, 6, 8, 12, 18 and 24 months after EOT (allowable window of + 10 days. Blood samples collected for PCR shall be immediately added to a tube containing one volume (5mL) of a solution of Guanidine/ClH 6M EDTA 0.2M pH 8,0 Buffer (GEB). Samples

with guanidine buffer can remain at room temperature. Trained nurses will be responsible for the blood collection, sample processing and storage.

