8.5 Follow up visit

During the follow-up phase, visits will be made every six months, regardless of the assigned study branch. At each visit, the following will be carried out: directed anamnesis, physical examination, EKG and determination of the parasitic DNA by PCR. Depending on evolutionary electrocardiographic changes and availability, an echocardiogram may also be requested. The times of visits will be in month 1, 4, 6, 8, 12 and 18 after the end of treatment (with a window of +/- 10 days).

EQ-5D-3L and cost-effectiveness questionnaires will be distributed to and completed by the participant during each visit.

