10.3 Statistical Analyses

Categorical variables will be presented as frequencies and percentages and continuous variables as median (interquartile range) or mean (standard deviation) according to the data distribution. Normality of distribution will be checked through histograms and the Kolmogorov-Smirnov test.

The chi-squared test or Fisher exact test will be performed to compare the frequencies across categorical variables and the Mann-Whitney test or Student t-test will be used to compare the continuous variables. Intention-to-treat analysis will be performed to evaluate the efficacy and safety that includes all participants randomized to the study groups. The primary analysis will compare proportion of patients with sustained negative PCR at 24 months in their randomly assigned treatment groups (intention-to-treat analysis). Moreover, the proportion of participants with adverse drug events will be also compared. Comparison analyses between groups will be performed using generalized linear models with a log-link

and binomial distribution. Longitudinal differences on quality-of-life scores between groups will be fitted using linear mixed models.

A per protocol analysis will also be performed. Those participants who do not comply with treatment or permanently interrupt or modify the proposed treatment will be excluded from the analysis unless they had a positive PCR prior to that time-point, in which case they will be included in the analysis and considered as a treatment failure.

For PCR analyses, means and bilateral 95% confidence intervals will be presented by group and visit. In addition, time to sustained parasite clearance until 6, 12, 18 and 24 months of follow-up visits will be assessed using Kaplan–Meier survival analysis with log rank test for significance. Repeated measures analysis will also be performed.

Statistical significance will be set at 0.025 for the non-inferiority outcome (positive PCR) and 0.05 for the superiority outcome (percentage of adverse drug reactions and QOL).

The interim analysis for early stopping will be based on superiority and conducted when all participants have reached 12 months of follow up since the end of treatment. An independent data and safety monitoring board (DSMB) will be convened for this study with expertise in CD, clinical trials as well as biostatistics. The purpose of the DSMB is to analyze the preliminary data at 12 months to help in the decision of interrupting any arm.

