11.8 Confidentiality of trial documents and participants' records

The investigator must assure that participants' anonymity will be maintained and that their identities are protected from unauthorized parties. On CRFs or other documents submitted to the Sponsor, participants should not be identified by their names, but exclusively by an identification code. The investigator should keep a participant enrolment list showing codes, names, and addresses. The investigator should maintain documents for submission to Sponsor authorized representative, and participant's signed written consent forms, in strict confidence.

12. Schedule of Activities

	Screening visit D-21	Baseline visit D0	Treat V S2 D14 (+/-2d)	Treat V S4 D28 (+/-2d)	EOT V S8 D56 (+/-7d)	Follow up Visits 1, 4, 6, 8, 12 and 18 months after EOT (+/-10 d)	End Visit 24 months after EOT (+/-15d)	Adverse Event Visit (not scheduled)	
Informed Consent Form	X								
Demographic data	X								
Medical History	X								
Toxic habits	X								
Chagas disease interview	X								
Concomitant medication	X	X	X	X	X	X	X	X	
Clinical interview	X	X	X	X	X	X	X	X	
Physical exam	X		X	X	X	X	X	X	
Pregnancy test ¹	X				X				
Hematology ²	X		X		X			X	
Biochemistry ³	X		X		X			X	
EKG	X					X	X		
Echocardiography ⁴	X					X	X		
Serology	X						X		
PCR	X					X	X		
Adverse			X	X	X			X	

events ⁵										
Randomization ⁶		X								
Treatment administration ⁷		X	X	X						
WHOQOL BREF Questionnaire ⁸		X						X		
EQ-5D-3L questionnaire ⁸		X	X	X	X	X	X			
Cost-effectiveness Questionnaire		X	X	X	X	X	X			

Treat. V: Treatment visits; **EOT V:** End of treatment visit; **EKG:** Electrocardiogram; **PCR:** Polymerase Chain Reaction.

1. Only women of childbearing age with potential to become pregnant. Baseline visit may be performed at the same time as the screening visit.
2. Red and white cell count.
3. Alanine aminotransferase (ALT); aspartate aminotransferase (AST); urea and creatinine.
4. Echocardiography will be performed in participants with EKG alterations at baseline annually or when new EKG abnormalities appear during follow up.
5. Serious adverse events (SAE) reporting period initiates upon participant enrolment (after signature of informed consent form); adverse event (AE)/ adverse event of special interest (AESI) reporting from administration after first dose of trial medication at Day 1.

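### Efficacy end of treatment is defined by arm, but all post-treatment PCR draws are timed from day 56; a log-rank analysis run on the arm-specific clock would make the short arms look slower to clear

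*Protocol*

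**What the plan says.** Three parts of the protocol bear on this.

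- **Efficacy definition.** Section 10.8: "For efficacy assessments, the EOT of each treatment arm will be defined according to the duration of the arm dosing regimen". With active dosing of 2, 4 and 8 weeks this means day 14, 28 and 56.
- **Sampling schedule.** Section 12 has a single EOT visit, at week 8 (day 56, ±7 days), for all participants. Section 7: "Blood samples for PCR will be collected at screening visit and at 1, 4, 6, 8, 12, 18 and 24 months after EOT". Section 8.5 says that follow-up "visits will be made every six months, regardless of the assigned study branch". Section 3.1 explains that, because of the blind, everyone is sampled at every visit. Section 6.1 fills the dosing to eight weeks in both short arms: active drug "for 2 weeks matching with placebo tablet administered in three daily doses for 6 more weeks" in Group A and "for 4 weeks matching with placebo tablet administered in three daily doses for 4 more weeks" in Group B. The schedule shows no PCR at day 14, 28 or 56.
- **Analysis.** Sections 10.3 and 10.8 both plan that "time to sustained parasite clearance until 6, 12, 18 and 24 months of follow-up visits will be assessed" by Kaplan-Meier with a log-rank test. This is in addition to the primary comparison of the proportion with sustained negative PCR at 24 months.

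**The concern.** The draws cannot follow the arm-specific EOT. A month-1 visit in the 2-week arm would fall near day 44 (14 + 30), during placebo dosing, and would reveal the allocation. So the draws are tied to day 56 while the efficacy clock starts at day 14, 28 or 56.

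After screening, clearance can first be seen at the draw one month after day 56. For most participants the recorded time to clearance is then simply the time from the origin to that draw. If the origin differs by arm, the offset becomes the event time. A planned significance test could then report slower clearance on the regimens under test when the parasitological results are the same.

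**Working it through.** **Inputs.** EOT by arm: day 14, 28, 56 (Sections 6.1 and 10.8). Draws: day 56 plus 1, 4, 6, 8, 12, 18 and 24 months (Sections 7 and 12), with one month taken as 30.44 days. Arm size: 224 randomised, or 134 if only the PCR-positive 60% count (0.60 × 224 = 134.4), from Section 10.1.

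**The plan's own figure.** Nothing here disputes the sample size, and it reproduces. With failure rates of 10% and 12%, a 15% margin, one-sided 0.025 and 90% power:

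n = (0.10 × 0.90 + 0.12 × 0.88) × (1.960 + 1.282)² / (0.15 − 0.02)² = 121.6, so 122 per arm.

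122 / 0.60 × 1.10 = 223.7, so 224.

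**Step 1: the offset.** Time on the efficacy clock = draw day − arm-specific EOT.

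| Draw (months after day 56) | 2-week arm | 4-week arm | 8-week arm |
|---|---|---|---|
| 1 | 72 | 58 | 30 |
| 6 | 225 | 211 | 183 |
| 12 | 407 | 393 | 365 |
| 24 | 772 | 758 | 730 |

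The offset against control is 56 − 14 = 42 days and 56 − 28 = 28 days at every draw. With a ±10-day visit window, first-draw times span 62–82, 48–68 and 20–40 days, so neither short arm overlaps the control arm.

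**Step 2: one case by hand.** Take 224 per arm, with 202 (90%) cleared at the first draw in each, comparing the 2-week arm with control.

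- Day 30: 448 at risk, 202 events, all in control. Expected: 101 per arm. Variance: 202 × 246 / 447 × 0.25 = 27.79.
- Day 72: at risk 224 (2-week) and 22 (control), 202 events, all in the 2-week arm. Expected: 202 × 224 / 246 = 183.9 and 18.1. Variance: 202 × 44 / 245 × (224 × 22 / 246²) = 2.95.
- Totals: observed 202 and 202; expected 284.9 and 119.1. Chi-square = 82.9² / 30.75, about 223.7.

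The log-rank test uses only the order of the times, so the 28-day offset of the 4-week arm gives the same 223.7. With 30 per arm the statistic is still 29.1.

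**Step 3: simulation under identical clearance.** Three arms, 400 trials per scenario, draws jittered by ±10 days, level 0.05.

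| Scenario | n per arm | Arm-specific EOT | Day-56 origin | Nominal visit |
|---|---|---|---|---|
| 85% clear at first draw, 90% overall | 224 | 100% | 5% | 5% |
| same | 134 | 100% | 3% | 4% |
| 50% clear at first draw, 90% overall | 224 | 95% | 6% | 5% |
| same | 134 | 78% | 7% | 4% |
| Event = first positive PCR, 10% or 20% failures | 134 or 224 | 6–10% | 5–7% | 5–7% |

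At a true 5% the simulation standard error is √(0.05 × 0.95 / 400) = 1.1 points, so the last two columns are consistent with the nominal level.

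**The case against.** The strongest reply is that no sentence says survival time is counted in days from the arm-specific EOT. The Kaplan-Meier sentence is worded around follow-up visits, PCR results are to be shown by group and visit, and the time origin is often settled in the statistical analysis plan. This stands as far as it goes: with curves indexed by nominal visit the false difference disappears. But the protocol does more than stay silent. It sets a rule for efficacy assessments and names the analysis. A statistical analysis plan that follows the rule inherits the problem, and one that departs from it contradicts the protocol.

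Some stronger readings are tempting and are not supported:

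- *The log-rank comparison is bound to show a difference.* It does so only if actual time from the arm-specific EOT is used.
- *Rejection is certain.* The 100% depends on most clearance appearing by the first draw, which the protocol does not state.
- *Short-arm draws fall outside their visit windows.* The windows belong to the schedule, whose EOT is day 56 in all arms. A draw made on schedule is in window whatever the arm.
- *The non-inferiority conclusion is biased.* It compares proportions at the same final visit and does not rest on the log-rank test.
- *The event should become first positive PCR.* Section 10.3 does define treatment failure as at least one positive PCR, and with that event rejection is only 6% to 10%. But the survival sentence names clearance, and changing the event is a preference.

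Time since the last active dose is also a legitimate descriptive scale, so the definition need not be removed altogether.

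**Conclusion.** The point holds in conditional form. Two definitions of EOT coexist, and the protocol does not say which one starts the clock for the secondary time-to-clearance analysis. Read literally, Section 10.8 shifts the short arms by 42 and 28 days. Under identical clearance this produces a false log-rank difference against them in about 78% to 100% of simulated trials, compared with 3% to 7% under a common origin or nominal visits.

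The range rests on assumptions that are not in the protocol: 50% to 85% clearing at the first draw with 90% overall, a log-rank level of 0.05, and no dropout. The direction does not depend on the exact pattern, because the control clock always starts later. The primary analysis is largely unaffected. This should be corrected, but it does not threaten the trial's main result.

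**What to change.** Reconcile Section 10.8 with the schedule in Section 12. Restrict the arm-specific EOT to describing exposure. State that all time-to-event and by-visit PCR analyses use one origin in every arm, either randomisation or the day-56 visit, indexed by nominal visit. Discrete-time or interval-censored methods suit the visit-based data and are an option. Use the same reference day where Section 10.8 (interim analysis) and Section 14 (stopping rule) speak of 12 months after treatment.

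The cost is a few lines in Sections 10.3 and 10.8 and matching wording in the statistical analysis plan. It needs no new data or visits and poses no risk to the blind. One small downside remains: with a common origin, visits fall at slightly different times after the last active dose. At the final visit these are 772.5 / 30.44 = 25.4, 758.5 / 30.44 = 24.9 and 730.5 / 30.44 = 24.0 months in the 2-, 4- and 8-week arms. They can be reported descriptively.
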